13.4 Routine Adverse Event Reporting

Note: The guidelines below are for routine reporting of study specific adverse events on the City of Hope case report forms and do not affect the requirements for CTEP-AERS reporting.

Routine reporting is accomplished via the Adverse Event (AE) Form. For this study, routine reporting will include all toxicities reported via CTEP-AERS and all Grade ≥ 2 AEs that can be attributed *probably or definitely* to the study drug in either study arm.

For all Grade ≥ 3 toxicities that can be attributed *probably or definitely* to the study drug in either study arm, the patient will be unblinded and taken off protocol therapy. (See [Section 5.0](#) for emergency unblinding.)

A City of Hope Adverse Event (AE) collection form will be submitted by study personnel on Days 180, 365, 540, and 730.

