4.3.2 Subjects on Dose Level 1 (3.125 mg/Placebo Daily)

At two weeks post-randomization, subjects will return to clinic for a clinical evaluation. During that visit, there will be two options:

- Increase to level 2, *or*
- If dose escalation is considered inadvisable by the investigator, to discontinue the study drug.

Subjects unable to tolerate dose level 1 should be taken off therapy per [Section 8.0](#). Adverse events that occur within 30 days of study drug discontinuation must be reported and followed to resolution. Adverse events considered to be of suspected or probable or definite relationship to study medication will be reported and followed to resolution whenever they occur (see [Section 8.1](#)). The reason for removal from protocol therapy will be recorded.

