9.3.3 Objective Safety Measures

Adverse events. The number of Grade 2-4 toxicities observed will be tabulated by treatment arm. Differences by treatment arm will be evaluated using Fisher exact tests.

Biomarkers. Liver function measurements (Bilirubin, AST, ALT) will be treated as continuous variables. Study participants will be considered to have elevated liver function if the measurements at 6, 12, 18, and 24 months are above the upper limit of the institutional reference range and higher than baseline pre-treatment level. These data will be coded such that those who are greater than 2-times the upper limit of the reference range will be considered to be clinically significant (Grade 1 if asymptomatic and requiring no intervention; Grade 2 if minimal/local/non-invasive intervention required). The frequency of individuals with elevated liver function measures will be compared between treatment groups using an exact test on 2x2 tables, stratified on CYP2D6. Logistic regression analysis will also be used to compare the frequency of elevated liver function between treatments, adjusted for covariates. Linear mixed-effects model for normally distributed data will also be used to compare the trends in liver function levels between the treatment groups. Procs MIXED and GLIMMIX will be used for longitudinal analysis of normally and non-normally distributed data, respectively. Proc GENMOD will also be used for normally and non-normally distributed data.

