Voluntary withdrawals: We assume that the proportion of patients in the placebo arm who will withdraw voluntarily by 24 months is 20% (10%/year); of note, this is less than the assumed overall attrition rate of 15%/year because attrition could occur due to other reasons such as toxicities, cancer recurrence, etc. With 125 patients in each arm at baseline, using Type I error=0.05, the study will have 80% power to detect a >15% absolute difference in the voluntary withdrawal rates between the two study arms.

WITH AMENDMENT #4:

Adverse events: We assume the rate of Grade 2-4 toxicities in the placebo group to be low, at 5%. At the end of the study, assuming 56 individuals remaining in each arm (19% attrition/year from the 91/arm at baseline), the study will have at least 80% power to detect an adverse event rate of 24.7% in the carvedilol group based on Fisher's exact test and Type I error=0.05.

Adherence to therapy: We will examine the difference in adherence rates by comparing the percent adherence by treatment group. With 91 study participants at baseline per arm, assuming a constant adherence rate of 90% in the placebo group, a between-measurement correlation of 0.6, 19% yearly attrition, and 2-sided alternative, there will be 80% power to detect an adherence rate of $\leq 70\%$ in the carvedilol group.

Voluntary withdrawals: We assume that the proportion of patients in the placebo arm who will withdraw voluntarily by 24 months is 26% (13%/year); of note, this is less than the assumed overall attrition rate of 19%/year because attrition could occur due to other reasons such as toxicities, cancer recurrence, etc. With 91 patients in each arm at baseline, using Type I error=0.05, the study will have 80% power to detect a >21% absolute difference in the voluntary withdrawal rates between the two study arms.

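### The AE Form is filtered by drug attribution but the Grade 2-4 arm comparison and its 80% power statement are not, so the power of that comparison is undefined

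*Combined protocol and SAP*

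**What the plan says.** **Recording.** Section 13.4 puts on the AE Form the events reported via CTEP-AERS and "all Grade ≥ 2 AEs that can be attributed" probably or definitely to study drug, in either arm. The form is submitted on Days 180, 365, 540 and 730. Table B in Section 13.3 shows what CTEP-AERS adds: Grade 5 events of any attribution, and unexpected Grade 4 events rated possible or higher.

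**Analysis.** Section 9.3.3 states: "The number of Grade 2-4 toxicities observed will be tabulated by treatment arm". It continues: "Differences by treatment arm will be evaluated using Fisher exact tests". No attribution condition is given.

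**Power.** Section 9.4, in the text that applies with Amendment 4, assumes a 5% rate of Grade 2-4 toxicities on placebo and 56 participants per arm at the end of the study. It claims at least 80% power to detect an "adverse event rate of 24.7% in the carvedilol group" by Fisher's exact test at Type I error 0.05. It does not say whether the two rates are all-cause or attributed.

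**A second reporting rule.** Section 4.3.2, for participants stopped at dose level 1, requires adverse events within 30 days of discontinuation to be reported, with no attribution condition. Beyond that: "Adverse events considered to be of suspected or probable or definite relationship to study medication will be reported" whenever they occur. The term suspected appears neither in Section 13.4 nor among the categories of Table B.

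**The concern.** In a placebo-controlled trial the randomised arms show what the drug causes. If events reach the database only after a blinded site has judged them probably or definitely drug-related, the comparison inherits that judgement. Fatigue and dizziness, the two toxicities that Section 6.1.2 lists as common, are non-specific, and a blinded site could reasonably rate them possible. A Grade 2 or 3 event rated possible has no general route onto the form. Capture could also differ between arms if a visible effect, such as a slow heart rate, sways the rating.

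Aim 1.2.1 is to establish safety and tolerability, and the Section 9.3.3 table is the only planned CTCAE-graded comparison of adverse events between arms. Its result is hard to interpret if the recorded events are not the ones the analysis and power text describe.

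**Working it through.** **Inputs (Section 9.4, Amendment 4).** Placebo 5%; carvedilol 24.7%; Fisher's exact test; α = 0.05. Per arm, 91 × (1 − 2 × 0.19) = 91 × 0.62 = 56.4, so 56. Allocation is 1:1.

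**Step 1: reproduce the stated power.** With x and y the numbers of participants with an event on carvedilol and placebo,

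power = Σₓ Σᵧ Bin(x; 56, p_C) · Bin(y; 56, p_P) · 1{Fisher p(x, y) ≤ 0.05}.

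With p_C = 0.247 and p_P = 0.05 the two-sided test gives 80.0%, and 24.7% is the smallest rate on a 0.1-point grid that reaches 80%. The plan does not state sidedness for this test. One-sided gives 88.8%, so two-sided is the version that matches. The plan's arithmetic is correct for unfiltered rates of 5% and 24.7%.

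**Step 2: treat 5% and 24.7% as all-cause rates and apply the filter.** The documents give no capture share, so every share below is an assumption.

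(a) The same share q is captured in both arms: p_P = 0.05q, p_C = 0.247q.

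| q | placebo | carvedilol | power |
|---|---|---|---|
| 0.9 | 4.5% | 22.2% | 73.6% |
| 0.7 | 3.5% | 17.3% | 56.6% |
| 0.6 | 3.0% | 14.8% | 46.3% |
| 0.5 | 2.5% | 12.4% | 35.1% |
| 0.3 | 1.5% | 7.4% | 12.1% |

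Power falls below 40%, half the stated value, somewhere between q = 0.6 and q = 0.5.

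(b) Background is captured at share b, and the drug excess (24.7 − 5 = 19.7 points) at share e: p_P = 0.05b, p_C = 0.05b + 0.197e.

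| b | e | placebo | carvedilol | power |
|---|---|---|---|---|
| 0 | 1 | 0% | 19.7% | 97.6% |
| 0.25 | 1 | 1.3% | 21.0% | 92.4% |
| 0 | 0.75 | 0% | 14.8% | 85.4% |
| 0.5 | 0.75 | 2.5% | 17.3% | 67.0% |
| 0 | 0.5 | 0% | 9.9% | 47.8% |
| 1 | 0.5 | 5.0% | 14.9% | 28.5% |

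Power rises above 80% when the filter removes mainly background. It falls steeply when drug events are missed.

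**Step 3: treat 5% and 24.7% as attributed rates instead.** The 80% then already includes the filter. An all-cause count adds unrelated Grade ≥2 events, assumed independent, at rate u in each arm: p_P = 1 − 0.95(1 − u), p_C = 1 − 0.753(1 − u).

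| u | placebo | carvedilol | power of all-cause test |
|---|---|---|---|
| 5% | 9.8% | 28.5% | 64.2% |
| 10% | 14.5% | 32.2% | 52.7% |
| 20% | 24.0% | 39.8% | 36.5% |

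Which of Steps 2 and 3 applies depends on a definition that the plan does not give.

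**The case against.** A reader might infer that the comparison loses most of its power. The documents do not support that. It needs a common capture share below roughly 0.55, or a similar loss of true drug events, and no share is given. Attribution is meant to remove background, and if it does so with little loss of drug events, power rises. If 5% was meant as an attributed rate, the stated 80% already allows for the filter. The word toxicities does not settle this: Section 13.4 uses it both for attributed events and for CTEP-AERS reports, which include deaths of any attribution.

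A reader might also infer that events outside the filter are never collected. That is wrong too:

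- Section 8.1.1 requires full documentation of adverse events leading to withdrawal of study medication.
- Section 4.3.2 has the unfiltered 30-day rule for those stopped at dose level 1.
- Section 10.6.2 makes clinically significant ECG changes adverse events.
- The tolerability criteria in Section 4.3.1, including Grade 2 dizziness and flushing, are confirmed on the Dose Escalation Form.
- Section 11.4 covers procedures potentially related to the protocol.
- Sections 9.3.3 and 9.3.4 compare liver tests, the Symptom Log (eleven time points) and voluntary withdrawals by arm without attribution.

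These objections stand against any claim of a known power loss or of missing safety data in general. They do not remove the mismatch. The Symptom Log is a 0-4 bother scale and not CTCAE grading; ECGs after screening are scheduled only on Days 14 and 42; and the withdrawal and discontinuation routes cover only people who stop. Section 4.3.2 has a narrower scope than Section 13.4, so its different wording matters less than it first appears, but the two should still agree. The case report forms are posted elsewhere (Section 14.0), so whether attribution is already a field cannot be checked here.

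**Conclusion.** The point holds as a mismatch between what is recorded and what is analysed. Section 13.4 conditions the AE Form on blinded attribution, while Sections 9.3.3 and 9.4 describe and power a comparison with no such condition. Grade 2-3 events rated possible are generally lost to that table. The power of the comparison is undefined, not shown to be low: with 56 per arm it spans about 12% to 98% over the assumed shares shown, and it is 80% as stated only if the two rates describe the events actually recorded. The direction of any error in the 80% cannot be told from the documents. This should be corrected because it bears on a stated secondary aim and because events not recorded now may not be recoverable later. It does not affect the primary endpoint.

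**What to change.** 1. On the existing AE Form, at Days 180, 365, 540 and 730, record all Grade ≥2 adverse events in both arms, with attribution as a data field.
2. In Section 9.3.3, report both the all-cause and the attributed comparison by arm.
3. In Section 9.4, say which of the two the 5% and 24.7% rates and the 80% power refer to, and give the power of the other under stated assumptions.
4. Reconcile the reporting rules and attribution terms in Sections 4.3.2 and 13.4.
5. Say how participants followed under the present rule enter the all-cause table. Section 9.5.2 already counts 87 with data at all time points on 30 June 2020.

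The cost is some extra site data entry, with no new visits or tests. If 5% is an attributed rate, the all-cause test will have less power (64% or 53% with 5% or 10% unrelated events per arm), which is why both comparisons should be kept. Nothing here concerns which events lead to unblinding or to stopping study drug.

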13.5 Syndrome Reporting

Unless otherwise specified in this protocol, syndromes should be reported as a single event using the CTCAE term for the composite syndrome, and not as the individual events that make up the syndrome. For example, Tumor Lysis Syndrome should be reported under the composite definition rather than reporting the component events (hyperkalemia, hyperphosphatemia, hypocalcemia, hyperuricemia) separately.

14.0 RECORDS AND REPORTING

See the Case Report Forms posted on the COG web site with each protocol under “*Data Collection Documents*”. A submission schedule is included.

14.1 CDUS

This study will be monitored by the Clinical Data Update System (CDUS). Version 3.0. Cumulative protocol- and patient-specific CDUS data will be submitted quarterly to CTEP by electronic means. Reports are due January 31, April 30, July 31 and October 31. CDUS reporting is not a responsibility of institutions participating in this trial.

14.2 Data Safety and Monitoring Committee

To protect the interests of patients and the scientific integrity for all clinical trial research by the Children’s Oncology Group, the COG Data and Safety Monitoring Committee (DSMC) reviews reports of interim analyses of study toxicity and outcomes prepared by the study statistician, in conjunction with the study chair’s report. The DSMC may recommend the study be modified or terminated based on these analyses.

Toxicity monitoring is also the responsibility of the study committee and any unexpected frequency of serious events on the trial are to be brought to the attention of the DSMC. The study statistician is responsible for the monitoring of the interim results and is expected to request DSMC review of any protocol issues s/he feels require special review. Any COG member may bring specific study concerns to the attention of the DSMC.

The DSMC approves major study modifications proposed by the study committee prior to implementation (e.g., termination, dropping an arm based on toxicity results or other trials reported, increasing target sample size, etc.). The DSMC determines whether and to whom outcome results may be released

REFERENCES

5. van der Pal HJ, van Dalen EC, van Delden E, et al: High risk of symptomatic cardiac events in childhood cancer survivors. *J Clin Oncol* 30:1429-37, 2012
6. Adams MJ, Lipshultz SE: Pathophysiology of anthracycline- and radiation-associated cardiomyopathies: implications for screening and prevention. *Pediatr Blood Cancer* 44:600-6, 2005

APPENDIX I: CTEP AND CTSU REGISTRATION PROCEDURES

INVESTIGATOR AND RESEARCH ASSOCIATE REGISTRATION WITH CTEP

Food and Drug Administration (FDA) regulations and National Cancer Institute (NCI) policy require all individuals contributing to NCI-sponsored trials to register and to renew their registration annually. To register, all individuals must obtain a Cancer Therapy Evaluation Program (CTEP) Identity and Access Management (IAM) account at <https://ctepcore.nci.nih.gov/iam>. In addition, persons with a registration type of Investigator (IVR), Non-Physician Investigator (NPIVR), or Associate Plus (AP) must complete their annual registration using CTEP’s web-based Registration and Credential Repository (RCR) at <https://ctepcore.nci.nih.gov/rcr>.

RCR utilizes five person registration types.

- IVR — MD, DO, or international equivalent;
- NPIVR — advanced practice providers (e.g., NP or PA) or graduate level researchers (e.g., PhD);
- AP — clinical site staff (e.g., RN or CRA) with data entry access to CTSU applications such as the Roster Update Management System (RUMS), OPEN, Rave, acting as a primary site contact, or with consenting privileges;
- Associate (A) — other clinical site staff involved in the conduct of NCI-sponsored trials; and
- Associate Basic (AB) — individuals (e.g., pharmaceutical company employees) with limited access to NCI-supported systems.

RCR requires the following registration documents:

Documentation Required	IVR	NPIVR	AP	A	AB
FDA Form 1572	✓	✓			
Financial Disclosure Form	✓	✓	✓		
NCI Biosketch (education, training, employment, license, and certification)	✓	✓	✓		
GCP training	✓	✓	✓		
Agent Shipment Form (if applicable)	✓				
CV (optional)	✓	✓	✓		

An active CTEP-IAM user account and appropriate RCR registration is required to access all CTEP and Cancer Trials Support Unit (CTSUS) websites and applications. In addition, IVRs and NPIVRs must list all clinical practice sites and Institutional Review Boards (IRBs) covering their practice sites on the FDA Form 1572 in RCR to allow the following:

- Addition to a site roster;
- Assign the treating, credit, consenting, or drug shipment (IVR only) tasks in OPEN;
- Act as the site-protocol Principal Investigator (PI) on the IRB approval; and
- Assign the Clinical Investigator (CI) role on the Delegation of Tasks Log (DTL).

In addition, all investigators acting as the Site-Protocol PI (investigator listed on the IRB approval), consenting/treating/drug shipment investigator in OPEN, or as the CI on the DTL must be rostered at the enrolling site with a participating organization.

Additional information is located on the CTEP website at <https://ctep.cancer.gov/investigatorResources/default.htm>. For questions, please contact the RCR *Help Desk* by email at [contact].

CTSU REGISTRATION PROCEDURES

This study is supported by the NCI Cancer Trials Support Unit (CTSU).

Protocol Specific Requirements for Site Registration:

- IRB approval (For sites not participating via the NCI CIRB; local IRB documentation, an IRB-signed CTSU IRB Certification Form, Protocol of Human Subjects Assurance Identification/IRB Certification/Declaration of Exemption Form, or combination is accepted)

Submitting Regulatory Documents:

Submit required forms and documents to the CTSU Regulatory Office via the Regulatory Submission Portal on the CTSU website.

To access the Regulatory Submission Portal log in to the CTSU members' website, go to the Regulatory section and select Regulatory Submission.

Institutions with patients waiting that are unable to use the Regulatory Submission Portal should alert the CTSU Regulatory Office immediately at [name] in order to receive further instruction and support.

Checking Your Site's Registration Status

Site registration status may be verified on the CTSU members' website.

- Log on to the CTSU members' website;
- Click on *Regulatory* at the top of the screen;
- Click on *Site Registration*;
- Enter the site's 5-character CTEP Institution Code and click on Go.
 - Additional filters are available to sort by Protocol, Registration Status, Protocol Status, and/or IRB Type.

Note: The status shown only reflects institutional compliance with site registration requirements as outlined within the protocol. It does not reflect compliance with protocol requirements for individuals participating on the protocol or the enrolling investigator's status with NCI or their affiliated networks.

APPENDIX II: INTERIM MONITORING

ACTIVATION PROTOCOL:

Plans for Interim Monitoring for Toxicity

Table s1: One-sided interim stopping boundaries for interaction test for treatment effect, concluding carvedilol superiority if the conditions are met.

Analysis	After N completes study	Superiority Bounds (O'Brien-Fleming boundaries)	
		Reject H0 if test statistic greater than O-F bound	Reject H0 if test statistic p is less than nominal alpha
Interim #1	83	3.7103	0.0001
Interim #2	166	2.5114	0.0060
Final	250	1.9930	0.0231

In addition to efficacy assessment, two blinded interim analyses will be performed to evaluate futility - after approximately 33% and 66% of patients have been accrued and evaluated. Our futility boundaries are calculated by using the Lan-DeMets spending approach applied to the O'Brien-Fleming boundaries as applied to beta. If the test statistic does not fall within the O'Brien-Fleming boundaries as specified in Table below, the DSMC will continue to randomize subjects. However, if the test statistic falls outside of the O'Brien-Fleming boundaries at an interim analysis, the DSMC will discuss whether the patients are receiving no benefit from carvedilol and consider discontinuing randomization. The O'Brien-Fleming boundaries in the table below are considered "non-binding", meaning that the DSMC has the option, but not the obligation, of halting the study if the futility boundaries are crossed.

Table s2: One-sided interim stopping boundaries for interaction test for treatment effect, concluding that the carvedilol arm shows no improvement over the placebo arm.

Analysis	After N completes study	Futility Bounds (O'Brien-Fleming boundaries)	
		Reject H1 if test statistic less than O-F bound	Reject H1 if test statistic p is greater than nominal alpha
Interim #1	83	-0.2361	0.5933
Interim #2	166	1.1704	0.1209
Final	250	1.9930	0.0231

In both of the interim analyses and the final analysis, the intent-to-treat data set will be the primary analysis group. In the interim analyses, the data will be analyzed with consideration of missing data. In each interim analysis, we will examine the effects of both pattern mixture models and selection models to assess the validity of the main GEE model estimates and particularly the treatment effect. To stop the trial, it will not be sufficient merely to show a treatment effect in the main GEE model. We will also look for supporting evidence such as a corresponding robustness of effect in the unstructured mean model, the pattern mixture models and the selection models.

WITH AMENDMENT #4

Table s3: One-sided interim stopping boundaries for interaction test for treatment effect, concluding that the carvedilol arm shows no improvement over the placebo arm.

Analysis	After N completes study	Futility Bounds (O'Brien-Fleming boundaries)	
		Reject H1 if test statistic less than O-F bound	Reject H1 if test statistic p is greater than nominal
Interim #1	87	1.502	0.067
Final	114	1.960	0.025

In the interim analyses and the final analysis, the intent-to-treat data set will be the primary analysis group. In the interim analysis, the data will be analyzed with consideration of missing data. To stop the trial, it will not be sufficient merely to show a treatment effect in the main GEE model. We will also look for supporting evidence such as a corresponding robustness of effect in the unstructured mean model.

